In this phase 2 study, GKT137831 was well tolerated. The reporting rate of AEs was low with fewer than 50% of subjects reporting AEs during the course of the study. In GKT137831-treated subjects, most Treatment-Emergent Adverse Events (TEAEs) were self-limiting, mild in severity, not treatment-related and resolved rapidly. The most commonly reported AEs were events related to respiratory tract infections. Other reported events were single occurrences experienced by 1 or 2 GKT137831 subjects. There was no evidence of dose-related increase in the occurrence of TEAEs. The only notable safety finding was a statistically significant, albeit slight and non-clinically significant (~2.5 mm Hg) increase in diastolic blood pressure (DBP). A trend for a marginal (~3 mm Hg) increase in systolic blood pressure (SBP) was also observed, but did not reach statistical significance. Finally safety signals related to findings made in previous toxicology studies were not confirmed. In particular, there were no safety signals related to thyroid function, liver function, bone marrow function, or cardiac conduction. No bone marrow toxicity, cardiac toxicity, liver toxicity, or renal toxicity was observed.

Upon review of all available safety data, the evaluation of GKT137831 at doses up to 200 mg BID in 68 subjects with DKD indicated a good tolerability and safety profile of GKT137831 compared with placebo.

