#### Adverse Events of Special Interest:

Potential effect of GKT137831 on arterial blood pressure and its clinical relevance will be evaluated. Systolic and diastolic blood pressure values will be examined together with temporally associated blood pressure related events including adverse events and serious adverse events, changes in study drug administration and other related changes in concomitant medications. Medical history and other possible contributing risk factors will also be assessed. Results will be presented by treatment group and planned visit.

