5.4 SAMPLE SIZE JUSTIFICATION

A sample size of 34 randomly allocated and treated subjects within each treatment group with an overall sample size of 102 subjects will have 80% power to detect a 28% difference in the means of the percent change from baseline in serum GGT. A Wilcoxon Mann-Whitney test has been used for the sample size estimate because this represents the worst-case scenario with regards to the statistical power. A standard deviation of 30 for the active GKT137831 group and a standard deviation of 40 for the placebo group have been assumed based on a recent phase 3 clinical trial of OCA [1].

An overall two-sided Type I error of 5% has been considered for the sample size calculation. The Hochberg method will be used to adjust the alpha level for multiple comparisons. Therefore, the first dose level comparison at the final analysis will be tested against an alpha level of 0.04695 and the second dose level will be tested against an alpha level of 0.023475. The alpha level of 0.023475 has been used for the sample size calculation.

The sample size calculation assumes all subjects (including withdrawals) will be included in the analysis. As a result, there has been no adjustment for dropouts.

6 Statistical Considerations

The SAS system version 9.4 (or higher), will be used for all analysis, unless otherwise specified.

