- If a subject has experienced more than one adverse events coded to the same preferred term within a system organ class then the subject will be counted only once under the

maximum severity for that preferred term and within that system organ class. The maximal severity is defined as first death (the highest possible level of severity), then life-threatening followed by severe, moderate, and mild (the lowest possible level of severity).

If a subject has experienced any AE with a missing severity then the AE's grade will be imputed as the maximal reported grade over all AEs experienced by that subject (excluding death). If a subject has experienced any AE with a missing relationship then the AE's relationship will be assumed to be related to study drug.

Adverse Events of Special Interest (AESI)

Potential effect of GKT137831 on arterial blood pressure and its clinical relevance will be evaluated. Systolic and diastolic blood pressure values will be examined together with temporally associated blood pressure related events including adverse events and serious adverse events, changes in study drug administration and other related changes in concomitant medications.

Drug induced liver injury related events will be considered as AESI as well.

In addition, the medical history and other possible contributing risk factors will be assessed.

The following categories of AEs will be listed by subject:

- All adverse events
- All TEAEs
- All serious AEs
- All AEs leading to study drug discontinuation
- All AEs leading to study drug interruption
- All AEs leading to death
- All AESI

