8.10.3 Vital Signs

Vital signs include Pulse rate, Systolic Blood Pressure (SBP) and Diastolic Blood Pressure (DBP). Pulse rate, SBP and DBP values as well as change from baseline to each planned visit will be summarized with descriptive statistics by visit for each received treatment group and for all received treatment groups combined.

The shift from baseline to each planned post-baseline visit for each of the criteria specified in Table 2 will be summarized by post-baseline visit for each received treatment group and for all received treatment groups combined.

Vital Sign	Criteria	Flag
	< 55 bpm	Low (L)
Pulse Rate	≥ 55 to ≤ 100 bpm	Normal
	> 100 bpm	High (H)
	< 90 mmHg	Low (L)
Systolic Blood Pressure	≥ 90 to ≤ 140 mmHg	Normal
	> 140 mmHg	High (H)
	< 45 mmHg	Low (L)
Diastolic Blood Pressure	≥ 45 to ≤ 90 mmHg	Normal
	> 90 mmHg	High (H)

Table 2: Vital sign values of clinical importance

Box plots will be produced to plot the vital signs change from baseline at each visit.

Vital signs (including Body Weight) will be listed by subject and visit with both conventional and Standard International values and all results considered abnormal as per criteria defined in Table 2 will be flagged.

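### Blood pressure is an event of special interest and the safety objective is comparative, yet the SAP pre-specifies no estimate of the blood pressure effect against placebo

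*SAP*

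**What the plan says.** SAP 8.10.3 plans this for vital signs: "Pulse rate, SBP and DBP values as well as change from baseline to each planned visit will be summarized with descriptive statistics by visit". The summaries are shown per arm as treated and for the arms together. The section adds shift tables against fixed limits (high means systolic above 140 or diastolic above 90 mm Hg), box plots of change, and flagged listings. Under SAP 6.6 the descriptives are n, mean, SD, median, minimum and maximum. Under SAP 6.5 baseline is a single value, the last one on or before the date of first dose.

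The special-interest text in SAP 8.10.1 reads: "Potential effect of GKT137831 on arterial blood pressure and its clinical relevance will be evaluated". Pressures are to be looked at together with related adverse events, changes in study drug and changes in other medication, along with medical history and risk factors. The SAP also names drug-induced liver injury as an event of special interest. The matching text in Protocol 10.4.3.4 ends: "Results will be presented by treatment group and planned visit".

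Three other places give the context:
- SAP section 4 and Protocol section 3 state the safety objective as a comparison with placebo.
- Protocol 2.1.5.2 reports from the earlier diabetic kidney disease (DKD) trial a statistically significant, "slight and non-clinically significant (~2.5 mm Hg) increase in diastolic blood pressure (DBP"), and a non-significant systolic trend of about 3 mm Hg. Protocol 2.2 says the finding may be chance or particular to DKD patients.
- Protocol 8.1.3 has pressure measured at every visit: Screening, Day 1, five on-treatment visits (Weeks 2, 6, 12, 18 and 24) and Week 28.

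**The concern.** Protocol 2.2 leaves a question open that this trial is placed to inform. It enrols a different population, and its upper dose of 400 mg BID is 800 mg a day, against at most 400 mg a day (200 mg BID) in the earlier trial. The data are there too: two pre-dose readings, five on treatment, and a concurrent placebo arm. The planned output never combines them. A mean shift of about 2.5 mm Hg is hard to see in one visit's arm means, and shift tables with cut-offs at 140 and 90 mm Hg respond weakly to a shift of that size.

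The stake is the form of the answer. Without a named contrast, baseline and time frame, the special-interest evaluation rests on reading several tables by eye, or on an analysis chosen after unblinding. SAP 8.7.2 already specifies a repeated-measures model with intervals for GGT, ALP, hsCRP, ALT, AST and total bilirubin, while saying that the study was not powered for secondary endpoints. Low power was therefore no bar to estimation there.

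**Working it through.** **The plan's own figure.** SAP 5.4 states "A sample size of 34 randomly allocated and treated subjects within each treatment group" and "80% power to detect a 28% difference in the means of the percent change from baseline in serum GGT". With its SDs of 30 (active) and 40 (placebo) and alpha 0.023475, 40,000 simulated Wilcoxon Mann-Whitney tests on normal data gave 79.7% power, so the stated 80% reproduces. No power or precision is stated for blood pressure.

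**Inputs.** From the documents: 34 per arm, five on-treatment visits, two pre-dose readings, and 2.5 mm Hg as the reference effect. Assumed, because the documents give no figure: between-subject SD s = 8-10 mm Hg for diastolic pressure; correlation r = 0.4-0.6, equal between all pairs of visits; a constant effect from Week 2; no dropout.

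**Formulas.** Variance per subject:
- (a) Single-visit change: 2s²(1 − r)
- (b) Single visit, adjusted for a one-value baseline: s²(1 − r²)
- (c) Single visit such as Week 24, adjusted for the mean of two baseline values: s²[1 − r²/((1 + r)/2)]
- (d) Five-visit mean, one-value baseline: s²[(1 + 4r)/5 − r²]
- (e) Five-visit mean, two-value baseline: s²[(1 + 4r)/5 − r²/((1 + r)/2)]

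SE = √(variance × (1/n₁ + 1/34)), with n₁ = 34 for one dose or 68 for both doses pooled. Half-width = 1.96 × SE. Chance of detecting 2.5 mm Hg = Φ(2.5/SE − 1.96).

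**Worked ends for (e), one dose.**
- s = 8, r = 0.6: 64 × (0.68 − 0.45) = 14.72; SE = √(14.72 × 2/34) = 0.931; half-width 1.82.
- s = 10, r = 0.4: 100 × (0.52 − 0.229) = 29.1; SE = 1.309; half-width 2.57.

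| Estimate | Half-width (mm Hg) | Chance of detecting 2.5 mm Hg |
|---|---|---|
| (a) one dose | 3.4-5.2 | 15-30% |
| (b) one dose | 3.0-4.4 | 20-36% |
| (c) one dose | 2.8-4.2 | 22-41% |
| (d) one dose | 2.15-2.85 | 40-62% |
| (e) one dose | 1.8-2.6 | 48-77% |
| (e) both doses pooled | 1.6-2.2 | 60-87% |

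By symmetry, the last column is also the chance that the interval excludes a 2.5 mm Hg rise when the true effect is zero. Rows (a) to (e) show where the gain arises: most comes from averaging over visits, less from baseline adjustment and the second baseline reading. A modelled Week 24 contrast alone stays wide (row c).

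**Are the assumed SDs plausible?** In the earlier trial, 68 of 136 subjects were on active treatment, so about 68 were on placebo. An unadjusted 2.5 mm Hg difference is then significant only if the SD of change is at most 2.5/(1.96 × √(2/68)) = 7.4 mm Hg. The assumed range gives change SDs of 7.2 to 11.0, hence z = 2.04 down to 1.33. It meets that result only at its favourable end, unless the earlier analysis was adjusted or used repeated measures. With SDs of change from 5 to 10 taken directly, a single-visit contrast per dose has a half-width of 2.4-4.8 mm Hg (t-based) and an 18-54% chance of detecting 2.5 mm Hg.

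**The case against.** The strongest defence is that nothing is lost for good. The planned tables give n, mean and SD of change per arm and visit, placebo included, so anyone can form an unadjusted difference and interval at each visit. The subject listings would let a repeated-measures estimate be produced later. All safety output in this plan is descriptive, a consistent choice for a phase 2 trial sized on GGT. Blood pressure is also to be reviewed with adverse events and medication changes, and an independent safety board sees unblinded data.

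Much of this stands, and it rules out several stronger readings:
- A reader might infer that the missing contrast is what stops the trial from confirming or excluding the earlier signal. The documents do not support that: per-visit contrasts are recoverable, and sample size is a large part of the limit even with the better model.
- A reader might infer that only by-arm descriptives are planned. Shift tables, box plots, listings and the joint clinical review are planned too.
- A reader might infer that blood pressure is the sole event of special interest, chosen because of the earlier diastolic rise. The SAP also names liver injury, and the link to the earlier trial is reasonable but stated nowhere.

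What the defence does not cover is the averaged effect. By-visit means and SDs lack the within-subject correlation needed for its interval and give no baseline adjustment. An analysis built later from listings would not be pre-specified.

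It is also fair that the comparison in half-width combines averaging with two changes of baseline; the table separates them. Dropout, unequal correlations or an effect that builds over time would reduce the gain.

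**Conclusion.** The gap is real but moderate. Neither document pre-specifies a treatment difference, interval, model or key time point for blood pressure, although it is an event of special interest under a placebo-comparative safety objective. No planned analysis is invalid and no efficacy conclusion changes.

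Under the stated assumptions, a five-visit adjusted average roughly halves the half-width for one dose. A true 2.5 mm Hg rise would still be missed in about a quarter to a half of trials per dose, and an absent one would fail to be excluded equally often. The gain is a sharper, pre-specified estimate, with no assurance that it settles the question. The figures are for diastolic pressure only; the documents give no SD from which to size the systolic contrast. The earlier rise was also judged not clinically significant, which bears on priority.

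**What to change.** Add to SAP 8.10.3 a repeated-measures model for diastolic and for systolic pressure on the Safety population, using on-treatment values from Weeks 2 to 24. Terms: treatment, visit, treatment-by-visit interaction, and the mean of the Screening and Day 1 readings as covariate. Report each dose minus placebo and pooled GKT137831 minus placebo, averaged over visits and at Week 24, with 95% confidence intervals. Label the output as estimation, with no multiplicity claim.

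State in the SAP that precision may not be enough to confirm or exclude a 2.5 mm Hg rise. Require the estimates to be read with the review of concomitant medication changes already planned in SAP 8.10.1, since blood-pressure treatment started or altered during the study could mask a rise.

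The two-value baseline departs from SAP 6.5, which allows exceptions for individual assessments, so it should be stated as one. If the single-value baseline is kept, the half-width per dose is about 2.15-2.85 mm Hg.

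Cost: two extra model-based safety tables from data already collected, of a model type already specified in SAP 8.7.2. The downside is that readers may take them as formal tests unless they are clearly labelled.

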8.10.4 ECG

ECG parameters include Heart Rate, QRS axis, PR interval, RR interval, QRS duration and QT interval.

In addition, QTcB interval and QTcF interval will be calculated based on the following formulae:

QTcB = QT interval/Square root of RR interval

QTcF = QT interval/Cubed root of RR interval

For all the above ECG parameters, the values as well as the changes from baseline to each planned visit will be summarized with descriptive statistics by visit for each received treatment group and for all received treatment groups combined.

For all the above ECG parameters, the number and percentage of subjects with abnormal results will be presented by visit for each received treatment group and for all received treatment groups combined.

In addition, the shift from baseline to each planned post-baseline visit in the overall ECG interpretation (normal, abnormal not clinically significant and abnormal clinically significant) will be summarized by post-baseline visit for each received treatment group and for all received treatment groups combined.

ECG parameters values will be listed by subject and visit and all results considered abnormal as per criteria defined in Table 3 will be flagged.

QTc Interval	Criteria (msec)	Flag
	≤ 30	Low (L)
Change from Baseline	> 30 to ≤ 60	Mid (M)
	> 60	High (H)
	> 450 to ≤ 480	Low (L)
Actual Value	> 480 to ≤ 500	Mid (M)
	> 500	High (H)

Table 3: Abnormal ECG -Criteria

For QTcB interval and QTcF interval, the categorized values at each visit and the categorized changes from baseline to each post-baseline visit will be summarized by post-baseline visit with the number and percentage of subjects for each received treatment group and for all received treatment groups combined. For both parameters, the categorized worst change from baseline over all planned post-baseline visits will be summarized similarly.

Box plots will be produced for each ECG parameter (Heart Rate, QRS axis, PR interval, RR interval, QRS duration, QT interval, QTcB interval and QTcF interval) showing change from baseline at each visit.

All ECG parameters values will be listed by subject and visit and all results considered abnormal as per criteria defined in Table 3 will be flagged.

9 Interim Analyses

An interim analysis is planned once at least 80-90% of the planned number of subjects to be randomized in the study have completed their Week 6 visit.

Only data collected for these subjects, prior to and including the date of the Week 6 visit for the last randomized subject included in the interim analysis cohort, will be taken into consideration for the interim analysis.

The purpose of the interim analysis is to support decision-making regarding the further development of GKT137831. It is not intended to amend the study protocol or stop the trial due to futility or overwhelming efficacy.

The primary efficacy endpoint of the interim analysis is the percent change from baseline to Week 6 visit in serum GGT.

The interim analysis will only be run on this primary efficacy endpoint and on the following secondary efficacy endpoints (no other endpoint will be analysed):

- Absolute change from baseline to Week 6 visit in serum GGT
- Absolute and percent change from baseline to Week 6 visit in serum levels of ALP
- Absolute and percent change from baseline to Week 6 visit in serum levels of hsCRP and fibrinogen
- Absolute and percent change from baseline to Week 6 visit in serum levels of ALT, AST, conjugated and total bilirubin.
- Absolute and percent change from baseline to Week 6 visit in the FIB-4 and APRI scores.

The interim analyses will also be run for the following 4 subgroups of interest:

- Subgroups of interest 1: subjects with GGT values below and above the stratification cut off value (≥2.5 x ULN) (for the primary efficacy endpoint of the interim analysis only). If only very few subjects have a Baseline GGT below 2.5 x ULN then the stratification cut off value for the analysis will be the median GGT at Baseline.
- Subgroups of interest 2: subjects below and above 65 years of age (for the primary efficacy endpoint of the interim analysis only)
- Subgroups of interest 3: subjects with ALP value below and above median at Baseline (for the primary efficacy endpoint of the interim analysis only)
- Subgroups of interest 4: subjects with hsCRP value below and above the ULN at Baseline (for the analysis of hsCRP only)

Subgroup summaries/analyses will only be performed for a minimum subgroup size of at least 20% of the interim analysis population, unless otherwise specified.

In addition, the gender and the age as well as the serum GGT, the serum levels of ALP, ALT, and hsCRP values will be summarized at Baseline for each allocated treatment group.

The interim analysis will be conducted by the unblinded SMB statistician, who has no involvement with the study conduct. The interim analysis outputs will be communicated to the Sponsor's Chief Medical Officer.

The interim analysis described above does not include assessments of safety data. The safety data will be reviewed periodically and separately as described in the study SMB charter.

10 Changes to Planned Analyses

The final analysis will be performed according to a 2-stage process detailed in Section 6.1.

11 Document History

Date	Version	Modified by	Brief details of changes made to template
150CT2018	1.0	[name]	Initial final version
15MAR2019	2.0	[name]	Updated final version The main changes are the following: 1. Addition of Section 6.1 to clarify the timing of the final analysis. 2. Addition of Appendix 1 to provide the list of Top Line tables.

12 References

[1] New Drug Application (NDA) 207999 submitted by Intercept Pharmaceuticals, Inc. for obeticholic acid (OCA) proposed for the treatment of Primary Biliary Cirrhosis (PBC), Gastrointestinal Drug Advisory Committee (GIDAC) Meeting, April 7th, 2016.

[2] Hirschfield GM et al. Efficacy of Obeticholic Acid in Patients With Primary Biliary Cirrhosis and Inadequate Response to Ursodeoxycholic Acid. Gastroenterology 2015; 148: 751-761.

[3] CTCAE v4.03:

http://evs.nci.nih.gov/ftp1/CTCAE/CTCAE_4.03_2010-06-14_QuickReference_5x7.pdf

13 Appendix 1: List of Top Line tables

Table order	Table number	Table title
1	14.1-1	Subject Disposition (Randomized Population)
2	14.1-3	Summary of Demographic and Baseline Characteristics (ITT Population)
3	14.1-5.1	Disease Characteristics (ITT Population)
4	14.2-1.1.1	Summary of Absolute and Percent Change from Baseline to Week 24 Visit in Serum GGT (ITT Population)
5	14.2-1.1.2	Analysis of Percent Change from Baseline to Week 24 Visit in Serum GGT (ITT Population)
6	14.2-1.3.1.1	Summary of Percent Change from Baseline to Week 24 Visit in Serum GGT by Subgroup of Baseline GGT values (ITT Population)
7	14.2-1.3.1.2	Analysis of Percent Change from Baseline to Week 24 Visit in Serum GGT by Subgroup of Baseline GGT values (ITT Population)
8	14.2-2.1.1	Summary of Absolute and Percent Change from Baseline to each Post- Baseline Visit in Serum GGT (ITT Population)
9	14.2-2.1.2	Analysis of Percent Changes from Baseline in Serum GGT across all Post Baseline Visits [a] Model Estimates (ITT Population)
10	14.2-4.1.1	Summary of Absolute and Percent Change from Baseline to each Post- Baseline Visit in Serum Level of ALP (ITT Population)
11	14.2-4.1.2	Analysis of Percent Change from Baseline to each Post-Baseline Visit in Serum Level of ALP Model Estimates (ITT Population)
12	14.2-5.1.1	Summary of Absolute and Percent Change from Baseline to each Post- Baseline Visit in Serum Level of hsCRP (ITT Population)
13	14.2-5.1.2	Analysis of Percent Change from Baseline to each Post-Baseline Visit in Serum Level of hsCRP Model Estimates (ITT Population)
14	14.2-7.1.1	Summary of Absolute and Percent Change from Baseline to each Post- Baseline Visit in Serum Level of ALT (ITT Population)
15	14.2-7.1.2	Analysis of Percent Change from Baseline to each Post-Baseline Visit in Serum Level of ALT Model Estimates (ITT Population)
16	14.2-8.1.1	Summary of Absolute and Percent Change from Baseline to each Post- Baseline Visit in Serum Level of AST (ITT Population)

Sponsor: Genkyotex Protocol: GSN000300 Statistical Analysis Plan:

Final version 2.0 / 15MAR2019

Table order	Table number	Table title
17	14.2-9.2.1.1	Summary of Absolute and Percent Change from Baseline to each Post- Baseline Visit in Serum Level of Total Bilirubin (ITT Population)
18	14.2-10.1.1	Summary of Absolute and Percent Change from Baseline to each Post- Baseline Visit in FIB-4 score (ITT Population)
19	14.2-10.1.2	Analysis of Percent Change from Baseline to Week 24 Visit in FIB-4 score (ITT Population)
20	14.2-11.1.1	Summary of Absolute and Percent Change from Baseline to each Post- Baseline Visit in APRI score (ITT Population)
21	14.2-11.1.2	Analysis of Percent Change from Baseline to Week 24 Visit in APRI score (ITT Population)
22	14.2-12.1.1	Summary of Change from Baseline to Week 24 Visit in Liver Stiffness (ITT Population)
23	14.2-12.1.2	Analysis of Change from Baseline to Week 24 Visit in Liver Stiffness (ITT Population)
24	14.2-12.2.1	Summary of Change from Baseline to Week 24 Visit in Liver Stiffness by Baseline Liver Stiffness Value Subgroup (ITT Population)
25	14.2-12.2.2	Analysis of Change from Baseline to Week 24 Visit in Liver Stiffness by Baseline Liver Stiffness Value Subgroup (ITT Population)
26	14.2-13.2.1.1	Summary of Change from Baseline to Week 24 Visit in Serum Level of Collagen Fragments (ITT Population)
27	14.2-13.2.1.2	Analysis of Change from Baseline to Week 24 Visit in Serum Level of Collagen Fragments (ITT Population)
28	14.2-15.2	Summary of Change from Baseline to Week 24 Visit in each Domain Score of the PBC-40 Questionnaire (ITT Population)
29	14.2-16	Summary of Change from Baseline to Week 12 and Week 24 Visits in Pruritus Score (VAS) (ITT Population)
30	14.2-17	PBC Responders Rates at Week 12 and 24 Visits Applying Two Response Criteria: Serum ALP < $1.67xULN$ and Combined Criterion Serum ALP < $1.67xULN$, ALP Reduction \geq 15%, and total bilirubin < ULN (ITT Population)

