The dog was the most sensitive species and the NOAEL was established at 150 mg/kg/day in the 26 week study. Treatment related effects in the dog studies were confined to ECG changes, effects on thyroid hormones, and effects on hematology parameters/bone marrow. Changes in liver function tests observed were generally considered to be of minimal severity and reversible and led to no liver pathologies and are consequently not considered to be of toxicological relevance. In the 28 Day study, QTc(F) prolongation was observed in high dose dogs (1000 mg/kg) and there was a single animal with an AV-block. The QTc prolongation was observed at both measurement times (Day 1 and Day 23) but the increase at the Day 23 reading was limited and seemed to affect only 2/6 treated high dose animals. Although there were no such ECG alterations observed in the 13 Week study, measurements in high dose dogs taken at Week 1 and 4 of the 26 Week study (animals still on 500 mg/kg/day) showed QTc (VdeW) increases of up to 20 msec. There were no QTc prolongation observed after the dose reduction to 300 mg/kg/day at week 13 and 26. The absence of any clear treatment-related ECG alterations at both the NOAEL of 150 mg/kg/day and the HTD (Highest Tolerated Dose) of 300 mg/kg/day in the 26 Week dog study and in already conducted clinical trials suggest that any such liability will not compromise subject safety in early stage clinical studies. Effects on bone marrow were seen at 500 mg/kg/day, the highest dose tested in the 26 week study and in one animal resulted in a severe non regenerative anemia which lead to euthanasia. Effects were restricted to the erythroid lineage and were preceded by a marked reduction in reticulocytes indicating the potential to monitor any potential effect in the clinic.

Reproductive toxicology studies have been performed in rats and rabbits. No treatment-related embryo-fetal findings in any dose group were seen in rats at doses of up to 1000 mg/kg/day. The NOAEL for maternal toxicity was established at 1000 mg/kg/day and for embryo-fetal toxicity was 300 mg/kg/day. In rabbits, GKT137831-related maternal mortality and severe effects on food consumption and body weight were seen at 1000 mg/kg/day, but there was no evidence of embryo-fetal toxicity at any dose level. The NOAEL for maternal and embryo-fetal toxicity was considered to be 300 mg/kg/day.

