# 5.3 Exclusion Criteria

A potential subject who meets any of the following criteria will be excluded from participation in this study:

- 1. A positive pregnancy test or breast-feeding for female subjects.
- 2. Any hepatic decompensation, defined as a past or current history of hepatic encephalopathy, gastrointestinal tract bleeding due to esophageal varices, or ascites.
- 3. INR > 1.2 unless subject is on anticoagulant therapy.
- 4. ALT > 3 x ULN.
- 5. Total bilirubin > 1 x ULN.
- 6. Planned or current plasmapheresis or other extra-corporeal treatments (e.g., MARS) for treatment-refractory pruritus.
- History of liver transplantation, current placement on a liver transplant list or current MELD score
  ≥ 15.
- 8. Cirrhosis with complications, including history or presence of: spontaneous bacterial peritonitis, hepatocellular carcinoma.
- 9. Hepatorenal syndrome (type I or II) or Screening serum creatinine > ULN.
- 10. Competing etiology for liver disease (e.g., hepatitis C, active hepatitis B, NASH, ALD, autoimmune hepatitis, primary sclerosing cholangitis, Gilbert's Syndrome).
- 11. Subjects receiving prohibited medications within 3 months of Screening (Visit 1) according to the list (a, b and c) provided in Section 6.6.2.
- 12. Treatment with any investigational agent within 4 weeks of Screening (Visit 1) or 5 half-lives of the IMP (whichever is longer).
- 13. A history of long QT syndrome.
- 14. Evidence of any of the following cardiac conduction abnormalities during the screening period:
  - A QTc Fredericia interval > 450 milliseconds for males and > 470 milliseconds for females.
  - A second or third degree atrioventricular block not successfully treated with a pacemaker.
- 15. A history of severe cardiovascular disease defined as any of the following within the 12 weeks preceding initiation of study treatment:
  - Acute myocardial infarction or unstable angina pectoris.

- A coronary revascularization procedure.
- Congestive heart failure New York Health Association (NYHA) Class III or IV.
- Stroke, including a transient ischemic attack.
- 16. History of cancer in the preceding 5 years, except adequately treated non-melanoma skin cancer, carcinoma *in situ* of the cervix, *in situ* prostate cancer, *in situ* breast ductal carcinoma, or superficial bladder cancer stage 0).
- 17. The occurrence of any acute infection requiring systemic antibiotic therapy within 2 weeks prior to Screening (Visit 1), or HIV infection.

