#### 12-lead ECG:

Heart rate, QT interval (both uncorrected and corrected using Bazett's and Fredericia's formulas), will be summarized using descriptive statistics by treatment group and planned visit.

Both the absolute values and the change from baseline will be considered.

Protocol No.: GSN000300	Compound No.: GKT137831
Protocol Version No.: Final 4.0; Amendment 3	Sponsor: Genkyotex
Protocol Date: 24 July 2018	Author: Cmed Clinical Services

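### SAP Table 3 flags every possible QTc change from baseline, so the abnormal flag, and any incidence table built on its change rows, cannot discriminate

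*SAP*

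**What the plan says.** SAP 8.10.4 names heart rate, QRS axis, PR, RR, QRS duration and QT as the ECG parameters and adds the derived QTcB and QTcF. Four of its provisions matter here.

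- **The criteria.** "Table 3: Abnormal ECG -Criteria" applies to QTc only. Change from baseline: 30 msec or less is Low (L), above 30 to 60 is Mid (M), above 60 is High (H). Actual value: above 450 to 480 is Low, above 480 to 500 is Mid, above 500 is High.
- **The listings.** In the by-subject listings, "all results considered abnormal as per criteria defined in Table 3 will be flagged". The section says this twice.
- **The incidence table.** "For all the above ECG parameters, the number and percentage of subjects with abnormal results will be presented by visit for each received treatment group". This sentence comes before Table 3 and does not refer to it.
- **The categorized summaries.** For QTcB and QTcF, "the categorized values at each visit and the categorized changes from baseline to each post-baseline visit will be summarized by post-baseline visit", with counts and percentages by arm. The worst change category over all planned post-baseline visits is summarized in the same way.

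The protocol's 12-lead ECG analysis paragraph (10.4.3.4) sets no abnormality cut-offs. It says only that heart rate and the QT measures "will be summarized using descriptive statistics by treatment group and planned visit".

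**The concern.** An abnormality table should leave normal results unmarked. The change block of Table 3 does not, because a subject whose QTc is unchanged or shorter receives an abnormal flag of Low. A reviewer scanning the listings would see a flag on every post-baseline QTc and could not use it to find the subjects who need attention.

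The second risk is in the incidence table. It promises counts of abnormal results for eight parameters, and the only numeric ECG criterion in the SAP covers two of them, QTcB and QTcF. A programmer must either apply Table 3, with an uninformative result for QTc, or devise a rule that the plan does not contain.

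The ECG output has some importance in this trial. Protocol 2.1.4 reports QTc prolongation in dogs at 1000 mg/kg and increases of up to 20 msec at 500 mg/kg/day. It also reports no clear treatment-related ECG change at 150 or 300 mg/kg/day, and the earlier phase 2 study showed no cardiac conduction signal. This is a reason to have a working flag. It is not evidence of a known problem in humans.

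**Working it through.** The documents state no expected incidence of abnormal QTc, so there is no figure to reproduce. The check is whether the rows of Table 3 can leave any result unflagged.

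**1. Change block.** Let *d* be the post-baseline QTc minus the baseline QTc, in msec.

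- Low: *d* ≤ 30
- Mid: 30 < *d* ≤ 60
- High: *d* > 60

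The union of the three rows is the whole number line, and the rows do not overlap. Every value of *d* therefore gets exactly one flag. For example, *d* = 0 and *d* = −25 are both Low. The share flagged is 100% whatever the distribution of *d*, so no assumption about its mean or spread is needed.

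**2. Actual-value block.** Let *q* be the QTc value. The rows are 450 < *q* ≤ 480, 480 < *q* ≤ 500 and *q* > 500. Values with *q* ≤ 450 carry no flag, so this block can discriminate. The two blocks follow different logic, and the letter L means an unremarkable change in one and a value above 450 msec in the other.

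**3. Comparison with Table 2.** The vital signs table in SAP 8.10.3 does the same job with a row labelled Normal, for example pulse rate "≥ 55 to ≤ 100 bpm". Laboratory abnormality in SAP 8.10.2 is likewise defined as lying outside the normal range. Only the QTc change block has no unflagged level, which suggests a drafting slip.

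**4. Effect on the listings.** Under Protocol 8.1.4, ECGs are recorded at Screening and at Weeks 2, 12 and 24, so Screening supplies the baseline. With 34 subjects per arm (SAP 5.4) and full attendance, each arm has 3 × 34 = 102 scheduled post-baseline records for each correction. All 102 carry a change flag. At Screening there is no change from baseline, so only the actual-value block applies.

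**5. Effect on the incidence table, if Table 3 is used.** A subject is abnormal at a visit if any row applies. One change row always applies to a subject with a baseline and a value at that visit, so the result among such subjects is 34/34 = 100% in each arm when all are assessed. The difference between any two arms is then 100% − 100% = 0, whatever the drug does.

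**6. Coverage of the incidence table.** It is promised for heart rate, QRS axis, PR, RR, QRS duration, QT, QTcB and QTcF, which is 8 parameters. Table 3 covers 2. The remaining 8 − 2 = 6 have no numeric criterion in the SAP.

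**The case against.** The strongest reply is that the plan already gives the safety reader what is needed. The categorized QTcB and QTcF summaries keep the three change bands as separate rows, and in such a table a row for 30 msec or less is simply the complement of the others. The worst change category, descriptive statistics and box plots are also planned. This stands. A reader might infer from Table 3 that changes above 30 and above 60 msec are hidden, but the same section shows that they are tabulated by arm.

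A second reply is that the incidence sentence does not cite Table 3, covers parameters that Table 3 does not address, and could rest on the local reading of the tracing. Both explicit links to Table 3 concern the listings. This stands in part: the SAP does not say that the incidence will be 100%. It does not remove the problem, because the overall ECG interpretation is a single reading per tracing, summarized separately, and gives no definition for each parameter. What remains is an undefined table, and the one numeric rule at hand gives 100% for QTc.

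A reader might also infer that the single 450 msec cut contradicts the protocol's sex-specific limits, "Fredericia interval > 450 milliseconds for males and > 470 milliseconds for females". It does not. Those are screening eligibility limits for QTcF, the protocol sets no analysis cut-off, and Table 3 also serves QTcB, for which the exclusion criterion sets no limit. An eligible woman between 450 and 470 msec would be flagged Low on the actual value. That is a reason for an optional display by sex and does not make the cut an error.

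**Conclusion.** The defect is real and of low severity. That Table 3 flags 100% of post-baseline QTc changes follows from its rows alone and rests on no assumption about the data. The consequence for the listings follows from the SAP's own words. The 100% incidence for QTcB and QTcF at each post-baseline visit is conditional: it holds if Table 3, with its change rows, is taken as the definition for the incidence table, and it applies to subjects with both a baseline and a post-baseline value. The lack of any numeric criterion for the other six parameters holds on either reading.

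The damage is confined to the flag and to any incidence table built on it. The documents do not support a claim that QTc information is lost, or that the absolute cut breaches a protocol rule. Efficacy, alpha and sample size are unaffected.

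**What to change.** Amend SAP 8.10.4 as follows.

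1. In Table 3, make a change of 30 msec or less an unflagged reference category, as Table 2 does with its Normal row. Keep it as a row in the categorized summaries.
2. State that, for QTcB and QTcF, abnormal in both the listings and the incidence table means a change above 30 msec (with above 60 shown separately) or an actual value above 450 msec (with above 480 and above 500 shown separately).
3. Restrict the incidence table to parameters with a stated criterion, or add criteria for heart rate, QRS axis, PR, RR, QRS duration and uncorrected QT.
4. Use different flag letters for the change and actual-value blocks, so that L does not carry two meanings.

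A display of the actual-value bands by sex is optional.

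The cost is a table edit, one or two clarifying sentences and a programming rule. Data collection and trial conduct do not change. The edit is best made before the first database lock described in SAP 6.1.
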